13.6 Analysis of Safety and Toxicity Data

Analysis set and grouping for the analyses: All patients who receive one or more doses of the drug combination will be included in the safety analysis. All listings and tables will be presented by treatment.

Adverse events (AEs): All adverse events recorded during the study will be summarized. The incidence of treatment-emergent adverse events will be summarized by treatment according to primary system organ class, severity based on the National Cancer Institute's Common Terminology Criteria for Adverse Events (CTCAE) version 4.0, type of adverse event, and relationship to treatment. Deaths reportable as SAEs and non-fatal serious adverse events will be listed by patient and tabulated by primary system organ class, type of adverse event, and dose level.

Laboratory abnormalities: All laboratory values will be converted into SI units, as appropriate, and the severity grade calculated using CTCAE, version 4.0. Parameters for which a grading does not exist will be classified into low/normal/high group by means of laboratory normal ranges. For each laboratory test (e.g., hematology, biochemistry) a listing of laboratory values will

be provided by laboratory parameter, patient and treatment group. The frequency of notable lab abnormalities (i.e., newly occurring CTCAE grade-3 or -4 laboratory toxicities), will be displayed by parameter, cycle, and dose level. Similarly, the frequency of all laboratory abnormalities will be displayed by parameter, worst CTCAE version 4.0 grade experienced and dose level. A separate listing will display notable laboratory abnormalities (i.e., newly occurring CTCAE grade-3 or -4 laboratory toxicities). Laboratory data will be summarized by presenting grade shift tables for those parameters for which CTCAE version 4.0 allows classification. All remaining data will be summarized by presenting shift tables based on normal ranges.

Laboratory data will be also be displayed by presenting summary statistics of raw data and change from baseline values (means, medians, standard deviations, ranges).

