7.5 Monitoring of Adverse Events and Period of Observation

All adverse events, both serious and non-serious, and deaths that are experienced by participants will be collected from the time of the first dose of study treatment up until 90 days after the last dose study treatment, or until death if death occurs first. The presence and resolution of AEs and SAEs (with dates) should be documented on the appropriate case report form and recorded in the participant's medical record to facilitate source data verification.

For some SAEs, the Overall PI or designee may follow-up by telephone, fax, and/or monitoring visit to obtain additional case details deemed necessary to appropriately evaluate the SAE report (e.g., hospital discharge summary, consultant report, or autopsy report).

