10. STUDY CALENDAR

Baseline evaluations are to be conducted within 2-weeks prior to start of protocol therapy. Scans must be done \leq 4 weeks prior to the start of therapy. All assessments must be performed prior to administration of any study medication. On days when TSH is required, TSH is not required to be resulted prior to administration of study medication. All study assessments and medications should be administered within \pm 3 days of the protocol-specified date, unless otherwise noted. Laboratory values do not need to re-meet eligibility criteria on Week 1, Day 1.

CONFIDENTIAL

This document is confidential. Do not disclose or use except as authorized.

BRAF ^j	X			X	X	X	X	X	X	X	X	X ⁱ	
PBMC ^k	X			X		X	(X)						
Tumor Biopsies ^k	X			X		X	(X)						
Rash Prophylaxis ^q		X ^q	X ^q	X ^q	X ^q								

- a. MAPK targeted therapy (MTT): In cohort 1, participants will be treated with the combination of dabrafenib and trametinib. In cohort 2, participants will be treated with trametinib. MTT will commence week 1, day 1 and be given continuously (except in the setting of toxicity) for two weeks in the lead-in phase and then 6-weeks in combination with pembrolizumab. Only if patients develop symptomatic or radiographic progression at anytime AFTER initial MTT-phase completion, then MTT may be resumed at a previously tolerated dose in combination with ongoing pembrolizumab.
- b. Participants will be seen on day 1 (+/-3 days) of week 1, week 3, and then every three weeks while remaining on therapy. If treatment is discontinued for a reason other than disease progression, study discontinuation, or withdrawal of consent, patients will be seen every 12 weeks (+/- 2 weeks).
- c. Dermatological examination done at screening, and within 1 week prior to dosing on week 9. A full-body skin examination and removal of pre-existing calluses and keratotic skin is recommended prior to initiation of study treatment (See Table 6-4).
- d. Ophthalmological examination done at screening and within 1 week prior to treatment on week 9. For Grade 2 visual changes or greater, an exam must occur within 24 hours of onset (or study team knowledge of the event). Consult ophthalmologist any time when patient reports visual disturbance. If there is visual loss or significant visual changes, consult ophthalmologist immediately (within 24 hours)
- e. Single EKG will be collected at screening and repeated on day 1 of weeks 3 and 6 in cohort 1.

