13. STATISTICAL CONSIDERATIONS

This is a phase II trial to assess the effect of adding an abbreviated MAPK-targeted therapy to pembrolizumab in patients with unresectable or metastatic melanoma. Two cohorts of patients will be enrolled and analyzed separately: Patients with BRAF^{V600} mutant melanoma, and patients with BRAF^{V600} wild-type melanoma. The trial will be based on parallel Simon two-stage designs according to disease cohort and will provide preliminary estimates of toxicity and efficacy.

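### The Section 13.6 adverse event tables pool events on resumed MTT with those of the planned 8-week course, so they cannot show the toxicity of the abbreviated regimen

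*Combined protocol and SAP*

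**What the plan says.** The trial's stated purpose is in Section 13: "This is a phase II trial to assess the effect of adding an abbreviated MAPK-targeted therapy to pembrolizumab". The abbreviated MTT course is defined in note a of the Section 10 calendar, where MTT is given "for two weeks in the lead-in phase and then 6-weeks in combination with pembrolizumab". Pembrolizumab alone follows, for up to two years.

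The same note covers progression after that course: "then MTT may be resumed at a previously tolerated dose in combination with ongoing pembrolizumab". It gives no maximum duration for the resumed MTT. The synopsis, Section 1.1 and Section 5.1 also build resumption into the design, and Section 5.5.1 says that progressing patients generally stay on the trial.

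Under Section 7.5, AEs "will be collected from the time of the first dose of study treatment up until 90 days after the last dose study treatment".

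Section 13.6 sets the safety population ("All patients who receive one or more doses of the drug combination will be included in the safety analysis"), the scope of the AE summary ("All adverse events recorded during the study will be summarized. The incidence of treatment-emergent adverse events will be summarized by treatment") and the grouping ("All listings and tables will be presented by treatment"). It defines neither 'treatment' as a grouping variable nor 'treatment-emergent'. It displays notable laboratory abnormalities by cycle but has no such split for AEs.

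The primary endpoint (Sections 1.2 and 13.1) does separate out resumed MTT: a patient who has restarted it does not count as having clinical benefit.

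**The concern.** A patient can pass through four different exposures: MTT alone, MTT with pembrolizumab, pembrolizumab alone, and MTT resumed after progression. A single incidence per AE over the whole study merges them. Each cohort receives one regimen, so the natural reading of 'by treatment' is by cohort, which does not separate the phases.

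Efficacy and safety would then describe different things. Efficacy is judged on the short MTT course, with resumption counted as failure. Safety would be tabulated over the short course plus whatever MTT follows that failure. Someone using the report to judge the toxicity of 8 weeks of MTT plus pembrolizumab could not recover it from the planned tables. Safety and tolerability is a listed secondary endpoint in Section 13.1.

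**Working it through.** **Stated figures.** The point contradicts no figure in the plan. The nearest safety calculation, Table 13.1, reproduces from 1 − (1 − p)^28: 0.245, 0.574, 0.762, 0.903, 0.929, 0.948 and 0.989 for true incidences of 1, 3, 5, 8, 9, 10 and 15%.

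**Do events on resumed MTT reach the tables?**
- Resumption is allowed within the protocol (synopsis, 1.1, 5.1, Section 10 note a).
- Progressing patients generally remain on trial (5.5.1), and the AE window runs to 90 days after the last study dose (7.5).
- Section 13.6 takes all recorded AEs, with no cut-off at progression or resumption.
- Suppose resumed MTT were held not to be study treatment. MTT restarted soon after the last pembrolizumab dose would still fall inside a 90-day window, which is longer than the planned MTT course of (2 + 6) × 7 = 56 days.

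**Do the other breakdowns in 13.6 separate them?** No. Relationship to treatment does not, because an event on resumed MTT is also treatment-related. Dose level, used for the serious AE tables, does not, because note a allows resumption at a dose tolerated before.

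**Direction.** Section 2.2.2.3 gives the median onset of first cutaneous squamous cell carcinoma (SCC) on dabrafenib monotherapy as Day 67 (range 9 to 217). At least half of those first events therefore came after more than 56 days. Longer MTT exposure adds first events of this kind. The example applies to the BRAF-mutant cohort, which receives dabrafenib. Under Section 7.1 SCC is reported as a serious AE, so the serious AE tables are affected too.

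**Exposure (assumed values).** Let f be the share of patients who resume and w the weeks of resumed MTT; neither is in the documents. Planned MTT per cohort is 25 × 8 = 200 patient-weeks. The resumed share of all MTT exposure is 25fw / (200 + 25fw). As a rough guide to f, the design's CBR values of 0.75 and 0.50 leave 25% and 50% of patients without benefit at week 24.

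| f | w | Resumed patient-weeks | Resumed share |
|---|---|---|---|
| 0.125 | 8 | 25 | 25/225 = 11% |
| 0.25 | 24 | 150 | 150/350 = 43% |
| 0.50 | 24 | 300 | 300/500 = 60% |
| 0.50 | 36 | 450 | 450/650 = 69% |

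**Incidence (assumed values).** Let a be the true incidence over the 8-week course. Let resumed MTT last k further 8-week periods at the same risk, so that r = 1 − (1 − a)^k. The tabulated incidence is a + f(1 − a)r.
- a = 5%, f = 0.125, k = 1: 0.05 + 0.125 × 0.95 × 0.05 = 5.6%.
- a = 5%, f = 0.50, k = 2: r = 0.0975, and 0.05 + 0.50 × 0.95 × 0.0975 = 9.6%.
- a = 10%, same two settings: 11.1% and 18.6%.

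In 25 patients, the 5% case is 1.25 true cases against 1.40 to 2.41 tabulated, an excess of about 0.1 to 1.2 patients. If a toxicity occurs only early, or recurs only in patients already counted, the excess is zero.

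**The case against.** **'By treatment' could mean by phase.** Section 5.5.1 describes the trial as having four treatment zones, which gives the term a possible by-phase sense. But Section 13.6 does not refer to those zones, and resumed MTT is not one of them: the fourth is follow-up after stopping pembrolizumab in complete response. This reading does not cure the gap.

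**Reporting everything is legitimate.** Resumption is part of the strategy, and an all-events table does not hide harm. This stands. The defect is that nothing beside that table isolates the regimen under test.

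**How much resumed MTT falls in the window is unsettled.** This also stands. The synopsis and Sections 1.1 and 5.1 word resumption as something that will happen, note a as something that may. Section 5.5 ends protocol therapy at progression unless 5.5.1 applies, and the criteria in 5.5.1.3 do not mention MTT.

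**No decision depends on the tables.** Safety is descriptive, without a comparator or a numerical toxicity limit in Section 13. That limits the consequence but does not remove the reporting gap.

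**A stronger reading.** A reader might infer a definite inflation factor. Take decreased ejection fraction at 5/55 on the full-dose combination (Section 2.2.2.4) and spread it at constant hazard over 41 weeks, the 9.4-month median PFS given there. The result is 1.8% for 8 weeks, against 3.0% to 6.3% if 25% to 50% resume for 20 to 41 weeks: a ratio of 1.6 to 3.4. The arithmetic is right but the documents do not support the inputs. Routine ejection fraction testing is only at screening and before week 9. Median PFS is not time on resumed drug. Patients without benefit may also die, leave, or continue pembrolizumab alone. Constant hazard is assumed, and with early clustering the ratio falls towards 1. Even as computed, the gap is 0.3 to 1.1 patients in 25.

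A reader might also infer that MTT is kept short mainly for tolerability. Section 2.3 raises tolerability chiefly for combinations with ipilimumab and rests the brief concomitant period on immune priming.

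**Conclusion.** The point holds as a gap in the planned tables. As written, Section 13.6 pools AEs on resumed MTT with those of the planned 8-week course plus pembrolizumab, so it cannot show the toxicity of the abbreviated regimen. The direction is upward for first occurrences of late-onset MTT toxicity. It is not established for common early events such as pyrexia, where a recurrence in a patient already counted adds nothing to any-grade incidence.

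The size is unknown. The 11% to 69% exposure share and the 5.6% to 9.6% incidence are illustrations that rest on assumed values of f, w and k, and on equal risk per 8-week period. For rare events the difference may be about one patient or fewer per cohort. The conclusion does not depend on those figures. It rests on the scope of 13.6, the collection window, and resumption being allowed within the protocol.

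**What to change.** Keep the all-events table. In Section 13.6:
- Define 'treatment-emergent', and replace the undefined grouping with cohort and treatment phase at AE onset: lead-in MTT; MTT plus pembrolizumab; single-agent pembrolizumab; after MTT resumption. Set phases from actual dosing dates, and say where dabrafenib continued alone under Section 6.2 belongs.
- Give AE and serious AE tables in that form, with patients at risk and patient-weeks for each phase.
- Add a regimen table per cohort that runs from first dose to the first dose of resumed MTT (or to the end of the collection window if MTT is not resumed), with later events shown separately. Late events of the 8-week course that surface on pembrolizumab alone then still count for the regimen.

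Reconcile the synopsis, Sections 1.1 and 5.1, Section 10 note a, and Sections 5.5 and 5.5.1.3 on treatment after progression, so that the start of the last phase is unambiguous. Which rule applies is for the investigators; the tables need only that there is one.

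The cost is analysis-plan wording and more tables, some with sparse cells. Section 7.5 already requires AE dates, and the primary endpoint already requires knowing whether and when MTT was resumed. No treatment or assessment changes.

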13.7 Reporting and Exclusions

13.7.1 Evaluation of Toxicity

Evaluation of toxicity. Define “evaluable.” For example: All participants will be evaluable for toxicity from the time of their first treatment.

13.7.2 Evaluation of the Primary Efficacy Endpoint

Evaluation of response. All participants included in the study must be assessed for response to treatment, even if there are major protocol treatment deviations or if they are ineligible. Each participant should be assigned one of the following categories: 1) complete response, 2) partial response, 3) stable disease, 4) progressive disease, 5) early death from malignant disease, 6) early death from toxicity, 7) early death because of other cause, or 9) unknown (not assessable, insufficient data). By arbitrary convention, category 9 usually designates the "unknown" status of any type of data in a clinical database.

All of the participants who met the eligibility criteria (with the possible exception of those who did not receive triplet therapy) should be included in the main analysis of the response rate. Participants in response categories 4-9 should be considered to have a treatment failure (disease progression). Thus, an incorrect treatment schedule or drug administration does not result in exclusion from the analysis of the response rate. Precise definitions for categories 4-9, and sometimes category 3, will be protocol specific.

All conclusions should be based on all eligible participants. Subanalyses may then be performed on the basis of a subset of participants, excluding those for whom major protocol deviations have been identified (e.g., early death due to other reasons, early discontinuation of treatment, major protocol violations, etc.). However, these subanalyses may not serve as the basis for drawing conclusions

concerning treatment efficacy, and the reasons for excluding participants from the analysis should be clearly reported. The 95% confidence intervals should also be provided.

APPENDIX A: PERFORMANCE STATUS CRITERIA

ECOG Performance Status Scale		Karnofsky Performance Scale	
Grade	Descriptions	Percent	Description
0	Normal activity. Fully active, able to carry on all pre-disease performance without restriction.	100	Normal, no complaints, no evidence of disease.
		90	Able to carry on normal activity; minor signs or symptoms of disease.
1	Symptoms, but ambulatory. Restricted in physically strenuous activity, but ambulatory and able to carry out work of a light or sedentary nature (e.g., light housework, office work).	80	Normal activity with effort; some signs or symptoms of disease.
		70	Cares for self, unable to carry on normal activity or to do active work.
2	In bed <50% of the time. Ambulatory and capable of all self-care, but unable to carry out any work activities. Up and about more than 50% of waking hours.	60	Requires occasional assistance, but is able to care for most of his/her needs.
		50	Requires considerable assistance and frequent medical care.
3	In bed >50% of the time. Capable of only limited self-care, confined to bed or chair more than 50% of waking hours.	40	Disabled, requires special care and assistance.
		30	Severely disabled, hospitalization indicated. Death not imminent.
4	100% bedridden. Completely disabled. Cannot carry on any self-care. Totally confined to bed or chair.	20	Very sick, hospitalization indicated. Death not imminent.
		10	Moribund, fatal processes progressing rapidly.
5	Dead.	0	Dead.

APPENDIX C: BIOASSAY

PROCESSING OF TISSUE SPECIMENS

Adapted from:

1. Leyland-Jones, B.R. et al. Recommendations for collection and handling of specimens from group breast cancer clinical trials. J Clinical Oncology, 26 (34): 5638-5644, 2008.

-Full guidelines from that manuscript are referenced on the World Wide Web at http://ctep.cancer.gov/guidelines/spec_bc_grptrials.html

2. University of Texas MD Anderson Cancer Center Institutional Tissue Bank Standard Operating Procedures, Version 7.0

MATERIALS/EQUIPMENT

Liquid Nitrogen in approved LN2 transport carrier	Surgical mask/eye protection
Safety glasses or face shield	Clean Laboratory coat
Freezer gloves	Clean protective shoes
Disposable latex gloves	Cryovials
Disposable scalpels or scalpel blades (or single edge razor blade)	Racks for cryovials
Forceps	Petri dish
Histoprep Marker	OCT cyro-compound
TissueTek cryomold	Kimwipes
10% Neutral Buffered formalin	100% Isopropanol
95% Ethanol (alcohol)	

HAZARDOUS MATERIALS

1. 10% Neutral Buffered Formalin

Formaldehyde : severe eye and skin irritant. Sensitizes by skin and respiratory contact. Toxic by ingestion and inhalation. Target organs effects on respiratory system. Corrosive. Carcinogen.

Emergency First Aid Procedures:	
Eye: Irrigate immediately with large quantity of water for a least 15 minutes. Get medical attention immediately
 
Skin: Flush with water for at least 15 minutes
 
Ingestion: Dilute immediately with water or milk. Induce vomiting. Call physician.

--	--

	Inhalation: Remove to fresh air. Give artificial respiration if necessary.
If released or spilled:	Use formaldehyde spill kit for small spills of 1000ml; For larger spills contact Environmental Health & Safety
Waste Disposal Method	Whatever cannot be saved for recovery or recycled should be disposed of according to local, state, and federal regulations.
Respiratory Protection	If the exposure level is exceeded, wear a full facepiece respirator equipped with a formaldehyde cartridge.
Ventilation	Work in well ventilated areas
Precautionary Labeling	Label with formaldehyde label
Handling and Storage Considerations	Wash hands thoroughly after handling. Avoid eye contact. Protect from freezing and physical damage. Store at controlled room temperature, 15-30° C.

2. Liquid Nitrogen

Emergency First Aid Procedures:	For Cold Liquid Frostbite: If any liquefied atmosphere gas contacts the skin or eyes, remove any clothing that may constrict blood circulation to the frozen area. Immediately flood or submerge the affected body area with large quantities of clean, unheated water and then apply cold compresses. A source of water should be nearby and easily accessible wherever liquid nitrogen activities are being conducted. If the skin is blistered, or there is any chance that the eyes have been affected, get the patient to a physician immediately for treatment.
	For Grogginess or Unconsciousness While Handling Liquid Nitrogen: If a person seems to become groggy or loses consciousness while working with liquid nitrogen, get him to a well-ventilated area immediately. Use a self-contained breathing apparatus if necessary. If breathing has stopped, apply artificial respiration. Whenever a person loses consciousness, call 911 immediately.
If released or spilled:	
Waste Disposal Method	
Respiratory Protection	
Ventilation	
Precautionary Labeling	
Handling and Storage	Use only containers specifically designed for holding

Considerations	liquefied gases
----------------	-----------------

FRESH/FROZEN TISSUE PROCESSING

Processing Options for Fresh/Frozen Tissue:

- OCT is especially useful for preserving histology, and may improve RNA recovery, and thus is recommended. A frozen section resulting from an OCT-embedded specimen will provide important information on the presence and quantity of tumor. Moreover, OCT prevents the tissue from desiccation and crumbling and also acts as an insulator from thermal change and limits ice crystal formation. If tissue samples are obtained by core (punch or needle) biopsies, each core should be separately embedded in the OCT.
- If OCT processing is not possible, controlled snap-freezing in cooled isopentane or with a heat extractor is recommended over simple dry-ice freezing. Snap-frozen specimens should be placed in an appropriate container (e.g., cryovial or cassette) and transferred to -80°C or colder for storage

Some guiding principles for fresh/frozen tissue collection include the following

- Do not slow-freeze. Samples should be snap-frozen. Slow freezing promotes the formation of ice crystals, which damage the nucleic acids (e.g., RNA) in the specimen. The slower a sample freezes, the larger the ice crystals. Older models of cryostats (bath/dewar or vacuum type) that require > one minute to freeze a specimen should be avoided.
- Do not place the specimen directly in liquid nitrogen. Instead, place the OCT-filled cryomold onto a stable structure (i.e. Petri dish) that is on the surface of the liquid nitrogen.
- If only dry ice is available, adding alcohol (e.g., isopropanol or ethanol) to the dry ice can make a slurry that will help freeze the specimen more effectively (the alcohol will increase the thermal conductivity of the dry ice). This, however, is not a preferred over liquid nitrogen for snap-freezing.
- Do not add serum to the specimen
- Do not touch the biopsy without sterile gloves
- Sterile or disposable equipment should be used, including for dissection and for snap-freezing.
- Instruments should be changed or cleaned between dissecting normal and tumor tissue.
- If a pen is used to label cryovials or other receptacles that will be stored in freezing conditions, ensure that the pen is waterproof/solvent-proof and can withstand long-term freezing conditions.
- Copies of any relevant pathology reports and material submission forms should be sent along with the specimens to the central bank. Reports should be coded

in a way they can be matched to the specimen(s) while also protecting patient confidentiality requirements.

- If possible, representative adjacent normal tissue should be provided in addition to the tumor tissue. Normal tissue should be maximally distant from the tumor (minimum 2 cm). Collection of germline DNA (i.e. from PBMCs) should be considered in all protocols that include the collection of tumor tissue for DNA isolation.

Size/Number of fresh/frozen biopsies

Punch biopsies (4-6 mm preferred, 2 mm minimum) of cutaneous and subcutaneous lesions are preferable to core needle biopsies. A single biopsy is generally sufficient for research purposes.

Core needle biopsies: It should be stressed that core biopsy – whether collected as fresh/frozen or FFPE – is superior to fine needle aspiration (FNA) (Singh, 2007). Cores are more representative than FNA, providing more accurate diagnostic information – including invasive versus in situ, grade, percent tumor, and other important histopathologic information. The minimum size for fresh/frozen tissue collection is generally 0.25 cubic cm, which is generally achieved with approximately four passes of a 14-gauge needle. In the diagnostic setting, the collection of 2-4 fresh/frozen cores for research is recommended, in addition to 2 cores for diagnosis. The fraction of cores that will contain viable tumor will decrease if/as the tumor shrinks in response to therapy. Therefore, fewer cores may be obtainable as lesions grow smaller.

If a previous biopsy site is noted in the specimen to be sampled, biopsies should not be taken from near that site. Core biopsies alter the biology of tissue – e.g., they introduce inflammatory material from wound reaction and biomolecules involved in wound healing – which can be problematic if a subsequent core taken from that tissue is used for assay development. Notably, genes involved in wound healing are very similar to those involved in cancer progression (Riss et al., 2006).

Fresh/Frozen Tissue Collection in the Surgical Setting

During surgery, fresh/frozen tissue may be acquired by the transfer of the surgical specimen from the operating room to the pathology department in a tumor container without fixatives. Once it arrives in the pathology department, the sample may be sectioned, and then cores taken with a punch biopsy instrument and snap-frozen. This method is preferred if ischemia time can be limited to 30 minutes or less. **Note:** use a sterile RNase free container if RNA work will be done with any of the tissue.

- *Alternative:* Taking cores and immediately freezing them in the operating room – i.e., a core biopsy is taken from the specimen immediately after the specimen is removed from the patient. Operating room acquisition of cores from the specimen right after excision helps keep ischemia time under 10 minutes, especially in situations where pathologists are some distance from the operating room.

Time to Freezing and Storage Temperature for Fresh/Frozen Samples

- Fresh tissue samples should be frozen as soon as possible. If they cannot be frozen immediately, they should be frozen within 30 minutes.
- Once snap-frozen, samples should be immediately transferred either to liquid nitrogen (preferred) or to a -80°C freezer. Specimens should be carried to such freezers on dry ice.
- Frozen samples should be stored long-term either in liquid nitrogen or in a locked freezer with a temperature of -80°C or colder. The freezer should be on electrical emergency power line and alarmed. If future uses of the tissue are unknown, storing the tissue in the vapor phase of liquid nitrogen will help to ensure long-term viability.
- Storage equipment may include small (2x3 inch) plastic, zip-top bags; mega-cassettes (for example, with each tissue or cryomold wrapped in aluminum foil); and cryoboxes and plastic racks (cryovial storage).

Quality Assurance for Fresh/Frozen Samples

A frozen section should be cut from the OCT block and stained with H&E to confirm tumor presence, percent of tumor cells, preservation of morphology, and the presence of any undesirable material, such as necrotic or inflammatory material. The H&E slide may be used as a guide to isolate specific portions of the sample for molecular analyses (i.e. viable tumor; adjacent normal tissue; etc).

Database Annotation for Fresh/Frozen Tissue Collection

When possible, the following should be recorded on the specimen submission form with respect to fresh/frozen tissue collection:

- Time before freezing: if >30 minutes, note time in 15-minute increments beyond 30 minutes.
- Freezing temperature
- If previous punch biopsy(ies) were performed on the patient or noted in the specimen
- Time point of sample – e.g., after which cycle of therapy

LABELING

Vials, including cryovials, should be labeled with the study name or number, a specimen ID number that is linked to the subject's study ID, contents of the vial, and date of collection. The subject's study ID should not be on the vial unless patient confidentiality is determined to be secure according to the clinical trial protocol. Specific procedures for labeling specimens should clearly be defined in the protocol. The central bank itself should have standardized labeling (printed or written) for archiving samples, such as unique sample IDs and or barcodes. The information included on a sample label must not include patient-identifying information, and should be compliant with the Health Insurance Portability and Accountability Act (HIPAA). The information should be sufficiently specific such that the encoded information (e.g., tracking number) can be linked to the sample in the database.

Recommended Procedures for OCT Embedding and Snap-Freezing

Specimen Preparation Prior to Fixation

- Using universal precautions, remove any excess blood from the tissue using a paper towel or KimWipe.
- Tissue should be cut on a dissection board using a razor blade or scissors with at least one dimension at a maximum thickness of 0.5 cm.
- Discard any unused tissue according to procedures for disposing of biological waste material.
- Discard the blade according to procedures for disposing of contaminating sharps.
- Weigh each section of the specimen prior to fixation
- For labeling, Markers specifically made for cryo temperatures are recommended (alcohol-based permanent markers will smudge).
- **Note:** if any of the tissue will be used for RNA work later use RNase free technique.

1. OCT Embedding

- a. Pre-Procedure Preparation: label cryomolds with permanent marker or printed cryolabel, and prepare (preferably print) sticker labels for foil wrappers. Labels should include sample ID number, tissue type, and date. Place cryomolds on a flat surface in a manner that will allow for easy differentiation of those intended for normal tissue and those for tumor tissue.
- b. When sample is available, fill the bottom of each cryomold with a thin layer (less than 1 mm) of OCT by slowly and carefully filling the mold. It is important to avoid formation of bubbles and avoid uneven surfaces.
- c. Weigh each section of the specimen prior to placing it in a cryomold. Record the weight in appropriate log and database
- d. If possible, pre-chill the prepared cryomold (step b). This can be done by: (1) setting on ice for 2-5 minutes, or (2) just prior to transferring specimen (step e) partially freezing by holding over liquid nitrogen until OCT starts to become cloudy.
- e. Transfer the specimen to the OCT-filled cryomold using forceps.
- f. Cover the tissue with OCT; ensure the top surface of the OCT compound completely covers the tissue and is level.
- g. The OCT can be hardened by placing a Petri dish on the surface of liquid nitrogen and, using forceps, place the filled cryomold in the Petri dish. Avoid allowing the cryomold to come in direct contact with the liquid nitrogen. Specimen(s) are sufficiently frozen when the OCT has become completely white and hard.
- h. After the OCT has hardened, place the mold in pre-labeled aluminum foil (heavy duty is best) with the appropriate label with the sample identification information.
- i. Place samples on dry ice until transferred to -80° freezer for storage.

2. Snap Freezing

- a. Pre-Procedure Preparation: Label 1.8 ml cryovials using a permanent cryo-marker (EtOH- and freezer-resistant).

- b. To determine specimen weight: record weight of the empty vial, add tissue, then re-weigh. Subtract weights to determine the weight of the specimen, and record.
- c. Place specimen in a 1.8ml cryovials using forceps. Use separate forceps for each type (tumor, normal) of specimen to avoid cross contamination.
- d. Tightly secure the cap and submerged in liquid nitrogen for “snap freezing”. Use freezer gloves and a face shield during this procedure. Take precautions to avoid accidental spillage or spattering of liquid nitrogen.
- e. Place samples on dry ice until transferred to -80° freezer for storage.

FFPE TISSUE PROCESSING

Fixation and paraffin infiltration

One fixative and one buffer type should be used across participating centers. All tissue samples should be fixed in 10% neutral phosphate-buffered formalin (i.e., 3.7% formaldehyde), pH 7. Resection specimens should be grossly dissected (macrosectioned) prior to fixation, to ensure adequate penetration of the fixative; ideally, the sections should be approximately 3 to 5 mm thick prior to placement in tissue cassettes for fixation. It is essential that surgical margins are appropriately marked and that these steps are carried out by a pathologist or their designate. Different blades should be used when dissecting normal tissue vs. tumor tissue. The time that elapses from resection to dissection and formalin fixation (the warm ischemia time) should be minimized, and typically should be no longer than 4 hours. Placing the specimen in fixative without dissection for overnight or longer is NOT adequate.

The following are recommended acceptable ranges of duration of fixation for FFPE specimens:

- Biopsies (core, needle, and skin biopsies): 8-24 hours
- Excision specimens: 12-24 hours in formalin (36 hours - absolute maximum)
- Tissue sections (0.25-1.0 grams): Overnight-24 hours in formalin (36 hours - absolute maximum)
- Weekend specimens: Although fixing and shipping of specimens over the weekend (i.e., Friday-Monday) is discouraged, if specimens must be left in formalin over the weekend, they should be oriented, “blocked”, bread-loaf sectioned and placed in a large amount of formalin in closed containers.

If the collecting center is not associated with a pathology group and does not have access to a tissue processor, then the specimen should be either 1) shipped in formalin on the day of collection for next-day delivery to the central bank, or 2) fixed in formalin for no more than 24 hours and then transferred to 70% ethanol, then shipped to the central bank within a few days. Samples should be protected from excessive heat when appropriate by packaging them in a styrofoam container (without ice packs). See Shipping section for more detailed information about appropriate packaging of samples.

The following are recommended ranges of time from formalin to paraffin on the processor (variable according to the specific manufacturer):

- 5-8 hrs for biopsies
- 6-14 hrs for other specimens (time depending on the instrumentation and tissue size)

